**List of abbreviations and relevant definitions**

EOC	Epithelial ovarian cancer
FIGO	International Federation of Gynecology and Obstetrics
SAE	Serious adverse event

## Summary

### Rationale:

As most cancers, ovarian cancer also spreads to regional lymph nodes. The concept of sentinel lymph node surgery is to see whether the cancer has spread to the very first lymph node or sentinel node. If the sentinel node does not contain cancer, then there is a high likelihood that the cancer has not spread to other lymph nodes. This means that, at least theoretically, a radical lymphadenectomy could be omitted and thus the associated morbidity. The sentinel node technique has been proven to be effective in other cancers such as breast cancer and malignant melanoma. In the gynaecological field it has been shown to be effective in vulvar cancer. Currently sentinel node studies are done for cervix and uterine cancer.

### Objective:

- 1) To determine whether or not a sentinel node procedure in patients with ovarian cancer is feasible when the tracers are injected in the ovarian ligaments.
- 2) To determine the anatomical localisations of the sentinel nodes.
- 3) To determine the incidence of false negative sentinel nodes.

**Study design:** phase I feasibility study.

**Study population:** the following patients will be included:

- Patients with a high suspicion of an ovarian malignancy in whom a median laparotomy and a frozen section analysis is planned.
- Patients with endometrial cancer in whom a staging laparotomy is planned.

**Intervention (if applicable):** After opening the abdomen, before starting the surgical staging procedure, blue dye and the radioactive-colloid will be injected in the ligamentum ovarium proprium and the ligamentum infundibulo-pelvicum. This will be done on the ovary with suspicion of malignancy (patients with an ovarian tumour) or one of the normal ovaries (patients with endometrial cancer).

**Main study parameters:** percentage of patients in whom it is feasible to identify sentinel nodes. Other study parameters are the anatomical localisation of the sentinel node(s) and the incidence of false negative lymph nodes.

**Nature and extent of the burden and risks associated with participation, benefit and group relatedness:** the surgery is prolonged with 20-25 minutes due to the required

incubation time after injection of the blue dye and radioactive isotope. A scintigram will be performed 24 hours after the surgery to determine whether residual radioactive lymph nodes

can be detected. The scintigram will only be performed if the patient is capable to be transported to the nuclear department. No extra blood samples will be taken, no extra visits, physical examinations or other tests are necessary. There is no risk of tumour dissemination by injecting the tracers in the ovarian ligaments. There is a 0,07 to 2,7% risk of an allergic reaction to the blue dye. The dose of radioactive isotope given does not give adverse side effects, either to the patients or the personnel present in the operating theatre.

## 1. Introduction and rationale

### ***Epidemiology***

Epithelial ovarian cancer (EOC) remains the tumour with the most unfavourable prognosis within the field of the gynaecological oncology. The incidence of ovarian cancer in the Netherlands in 2008 was 14.5 per 100.000, with 12.3 deaths per 100.000 [1]. In the US in 2007 the incidence was 13.0 per 100.000 and there were 8.2 deaths per 100.000 [2]. The high mortality rate is partially due to the fact that approximately 75% of patients is diagnosed with advanced stage EOC.

### ***Background***

EOC can metastasize through three different ways [3,4]: intraperitoneal (in the abdominal cavity), lymphogenous and haematogenous. Concerning the lymphogenous spread, it is clear that lymphatic metastases of EOC mainly occur in the para-aortic lymph nodes [5]. It is believed that the tumour cells follow the lymph vessels that accompany the ovarian artery and vein in the infundibulopelvic ligament up to the high para-aortic region and renal vein. Nevertheless, pelvic lymph node metastases are also frequently found [6-16]. These tumour cells probably follow a different route, following the para-uterine vessels in the broad ligament towards the uterine artery and vein and further on to the iliac vessels. In some case reports isolated inguinal node metastases are also described [17-20]. The exact mechanism of this route of metastasis is still unclear, but the metastatic cells might follow the course of the round ligament towards the inguinal lymph nodes, or might follow the iliac vessels towards the femoral vessels. The incidence of lymph node metastasis in clinical stage I-II ovarian carcinoma is 14.2% [21].

### ***Staging***

In case of a clinical early stage ovarian cancer, the Dutch guideline [1] recommends a staging laparotomy with adequate lymph node sampling, with an absolute minimum of ten lymph nodes removed. In the same guideline, a footnote is made stating that a larger number of removed lymph nodes will increase the chance of finding metastases. These lymph nodes also need to be sampled from different anatomical regions, of which the most important are the

para-aortic and paracaval region between the renal vein and inferior mesenteric artery, the common, internal and external iliac vessels and the obturator fossa.

### ***The clinical significance of staging***

According to the International Federation of Gynecology and Obstetrics (FIGO), EOC with lymph node metastases is classified as FIGO stage IIIC disease, even in the absence of peritoneal metastases [22]. In contrast to patients with FIGO stage I ovarian cancer after a comprehensive staging procedure, patients with a FIGO stage III ovarian cancer obtain adjuvant chemotherapy. Therefore, the recognition of lymph node metastases is of utmost importance.

Surgical staging of EOC and the extent of lymph node dissection differs greatly from centre to centre [23].

A review published in 2011 showed an incidence of 14.2% for lymphnode metastasis in early EOC [21]. The incidence is higher in the grade 3 tumours (20.0%) and the serous histological subtype (23.3%). Whereas in grade 1 and mucinous tumours this is respectively 4.0% and 2.6%.

### ***Methods for identification of lymph node metastases***

#### *Radiological imaging*

The assessment through radiological techniques (CT scan, MRI, PET) alone is not feasible. The sensitivity and specificity for detection of lymph node metastases in ovarian cancer of a PET scan are 73.2% and 96.7% respectively, of a CT scan 42.6% and 95.0%, and of a MRI 54.7% and 88.3%. [25].

#### *During surgery*

Removal of lymph nodes:

- systematic lymphadenectomy / lymph node sampling

Approaches range from taking some lymph nodes only (lymph node sampling) to systematic lymphadenectomy [22]. A systematic lymphadenectomy can be seen as the golden standard. However, such a radical procedure gives more late morbidity than lymph node sampling. These include the formation of lymphocyst (up to 13.5%), nerve and vessel injury (up to 4%) and increased blood loss and operating time [26, 27].

- removal of sentinel node(s)

Through a sentinel node procedure the first node that receives primary lymphatic flow can be identified (the so called sentinel node). The pathological examination is an indication of the nodal status of the remaining nodes. If the sentinel node is negative, the patient may be spared a radical lymphadenectomy and thus the morbidity that can be caused by it [28].

The sentinel node technique has been proven effective in other cancers such as breast cancer and malignant melanoma. In the gynaecological field it has been shown to be effective in vulvar cancer. Currently sentinel node studies are done for cervix en uterine cancer. Studies done for sentinel node in ovarian cancer are very limited. One article that describes the role of sentinel lymph node sampling in gynaecological cancers, only briefly mentions ovarian cancer. The authors state that the procedure is difficult due to the often bulky mass ovarian tumours. Furthermore, with injecting in the ovary there is a possible risk of tumour dissemination [28].

*Nyberg et al.* have done a study in 16 patients with high-risk uterine cancer in which technetium and blue dye were injected in the right or left ovary [29]. They used an incubation time of 15 minutes. In this study patients were included with a high-risk uterine carcinoma because these patients obtain the same operation as patients with clinical early stage ovarian cancer: a total abdominal hysterectomy (TAH) with bilateral salpingo-oophorectomy (BSO) and a pelvic and para-aortic lymphadenectomy or lymph node sampling. In 15 out of 16 patients the sentinel node was detected. Another study used activated charcoal solution to identify ovarian lymphatics in 11 patients. The charcoal was injected in the cortex of the ovary. The charcoal was deposited in the lymph nodes of all patients [12].

These studies all inject in the ovary, which gives a risk of tumour dissemination. In our feasibility study we are planning to inject in the ligaments of the ovary, not in the cortex itself. Therefore, besides patients with high risk endometrial cancer, we also can include patients with an enlarged ovary without risk of tumour dissemination.

The lymphatic mapping can be done with blue dyes as well as radioactive isotopes; both can be injected in the ovarian ligaments which contain the main routes of lymph drainage. After the incubation time the sentinel nodes should be visualized by either colorization (blue lymph nodes can be identified) and / or by the radioactive tracer [29]. Although in breast cancer radioactive isotope compared to blue dye shows a higher detection rate of the sentinel node [30], it has been shown that the detection rate is the highest when both radioactive isotope and blue dye are combined, instead of using them alone [30, 34].

The blue dyes can cause an allergic reaction, which can present itself from hypotension with urticaria and erythema to severe cardiovascular collapse with bronchospasm [28]. However, the incidence of an allergic reaction from blue dye is very low and varies from 0.07 to 2.7% [31].

The radioactive isotope is safe for the patient as well as the health care workers [35]. No allergic reactions are described due to the radio-active isotope.

### ***Conclusion***

This study is social relevant because in patients with clinical early stage ovarian cancer lymph node metastasis are found in 14.2%. A sentinel node procedure can prevent unnecessary radical lymph node dissection with it's associated morbidity. If this procedure proves to be effective, it is also more accurate than the at random sampling which is currently done in the Netherlands.

This study is scientific relevant since the research done for sentinel node procedure in ovarian cancer is very limited and so far limited to injection of tracers in the ovarian cortex with the possibility of tumour spread. Injection of tracer in the ovarian ligaments has, to our knowledge, never been published.

## **2. OBJECTIVES**

### ***Primary Objective***

To determine whether or not a sentinel node procedure in patients with ovarian cancer is feasible by injecting the tracers into the ovarian ligaments instead of into the ovary itself.

In this feasibility study we will include both patients with (suspicion of) ovarian cancer as well as patients with a high-risk uterine carcinoma. The latter group of patients can also be included because these patients obtain the same surgical procedure; a total abdominal hysterectomy (TAH) with bilateral salpingo-oophorectomy (BSO) and a pelvic and para-aortic lymphadenectomy of lymph node sampling.

***Secondary Objective(s)***

- The anatomical location(s) and number of the sentinel node(s):
  - visualized at surgery regarding blue dye
  - recorded by the gammaprobe at surgery radiocolloid
  - visualized at scintigraphy 24 hours after surgery regarding possibly remaining lymph nodes
- Incidence of false negative lymph nodes.

### **3. STUDY DESIGN**

Observational feasibility study to detect sentinel nodes: mapping the lymphatic drainage of the ovaries.

The study will end after 20 patients, of which at least 10 patients with ovarian cancer, are included in which the complete sentinel node procedure has been performed. The expected inclusion period is estimated to be two years. If the detection rate of the sentinel node is less than 50%, or when less 5 patients are included in a year, the study will end prematurely.

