***Sample size calculation***

Between 24 and 28 patients will be included in the study.

The sample size calculation is based on the fact that:

- with a group of 20 evaluable patients the study group is large enough to give an answer whether sentinel node(s) can be detected related to the ovarian lymphatic flow when the tracers are injected in the ovarian ligaments. For this purpose both patients with an ovarian and endometrial malignancy, planned for a staging laparotomy can and will be included.
- patients with a benign result on frozen section of the suspicious ovary will be excluded from the study because no lymph node(s) will be resected in these patients. These patients will be documented and described in the report after the study.
- based on retrospective data, in 60% of the patients with a suspicious ovary, frozen section will confirm a ovarian malignancy.
- to calculate one of the secondary endpoints (incidence of false negative sentinel lymph node) at least 10 patients with ovarian cancer should be part of the 20 evaluable patients.

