#### ***Withdrawal of individual subjects and replacement***

Subjects can leave the study at any time for any reason if they wish to do so without any consequences. The investigator can decide to withdraw a subject from the study for urgent medical reasons. Also patients with an ovarian tumour and benign result at frozen section during surgery will be excluded from the study.

These patients will be replaced by a new study subject until 20 completed sentinel node procedures are performed.

[figure not shown]

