***Interim analysis.***

For the surgeons there will be probably a learning curve for applying the injection and detecting the nodes, therefore initially the detecting rate of the sentinel node(s) in this pilot study should not be set to high. Nevertheless, an interim analysis will be done once we have included 10 patients in whom the sentinel node procedure could be performed. This will be done by one of the investigators. If less than 50% of the cases no sentinel node(s) could be detected the study will prematurely end.

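### Attempts that fail at injection or are abandoned may drop out of the feasibility rate, because the interim set, accrual and replacement all depend on the procedure having been performed

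*Protocol*

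**What the plan says.** The Summary gives the main study parameter as the "percentage of patients in whom it is feasible to identify sentinel nodes" and names no denominator. Four other places decide which patients stand behind that percentage:

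- **Section 3, Study design.** The study ends after 20 patients, at least 10 of them with ovarian cancer, "in which the complete sentinel node procedure has been performed".
- **Section 4, Sample size calculation.** The target is described as evaluable patients: "with a group of 20 evaluable patients the study group is large enough". Neither this term nor the complete procedure is defined.
- **Section 5, Withdrawal and replacement.** Three groups are named: subjects who choose to leave, subjects the investigator withdraws on urgent medical grounds, and ovarian patients with a benign frozen section. Then: "These patients will be replaced by a new study subject until 20 completed sentinel node procedures are performed".
- **Section 7, Interim analysis.** "an interim analysis will be done once we have included 10 patients in whom the sentinel node procedure could be performed". Under Premature termination in Section 5, the study stops if nodes are identified in fewer than 50% of patients at that look.

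Reasons for leaving are to be documented (Section 5, Follow-up of subjects withdrawn). Nothing says whether those patients enter the rate.

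**The concern.** Feasibility of injecting into the ovarian ligaments is the question the study asks, and this route is what is new about it. An attempt in which the ligaments cannot be injected, or which is abandoned because of the procedure, is a negative answer to that question. If patients enter the rate only once the procedure has been performed, the endpoint is conditioned on part of its own outcome. Any resulting error goes one way, towards a conclusion of feasible.

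The same selection acts on the futility check. Section 7 expects a learning curve in applying the injection as well as in finding nodes, so failed attempts, if there are any, would tend to fall among the early patients who decide whether the study continues.

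**Working it through.** **Inputs from the protocol.** 20 completed procedures (Section 3); at least 10 evaluable patients with ovarian cancer, 60% malignant at frozen section, and 24 to 28 included (Section 4); interim after 10 procedures with a 50% bar (Sections 5 and 7).

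**Inputs not given, assumed here.** The number k of attempts that fail at injection or are abandoned for procedure-related reasons, and the number D of patients with a detected node. The protocol states no target rate, alpha or power.

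**Step 1. Reproduce the planned inclusion.** The plan says "Between 24 and 28 patients will be included in the study". Using its 60% malignancy rate:

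inclusion = (ovarian evaluable)/0.6 + (endometrial evaluable)

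- 10 ovarian + 10 endometrial: 10/0.6 + 10 = 26.7, rounded up to 27.
- 12 ovarian + 8 endometrial: 12/0.6 + 8 = 28.
- The lower end, 24, needs 6/0.6 + 14, which has fewer than the required 10 ovarian patients.

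Benign frozen sections alone account for the upper part of the range. At the 10 + 10 mix, 28 − 27 leaves about one place for any other loss. No allowance for failed attempts is stated.

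**Step 2. Final rate.** Compare D/20 (completed procedures) with D/(20 + k) (all attempts, failures counted as not detected).

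| D | k = 0 | k = 1 | k = 2 | k = 4 |
|---|---|---|---|---|
| 12 | 60.0% | 57.1% | 54.5% | 50.0% |
| 15 | 75.0% | 71.4% | 68.2% | 62.5% |
| 18 | 90.0% | 85.7% | 81.8% | 75.0% |

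The relative inflation is (20 + k)/20: none at k = 0, 5% at k = 1, 10% at k = 2, 20% at k = 4. Clopper-Pearson 95% intervals at D = 18 are 68.3 to 98.8% for 18/20 and 59.7 to 94.8% for 18/22. The shift is modest beside the sampling error, but it is systematic.

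**Step 3. Interim decision.** 5/10 = 50% continues. One omitted failed attempt makes it 5/11 = 45.5%, and two make it 5/12 = 41.7%; both would stop. With six detections, 6/11 = 54.5% and 6/12 = 50% still continue. So with one or two omitted failures, the decision changes only when exactly five nodes were found in ten performed procedures.

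**Step 4. Chance of passing the interim.** Assume 10% of attempts cannot be performed and detection is 60% when they can. The rate per attempt is 0.6 × 0.9 = 0.54. The binomial chance of at least 5 in 10 is 83.4% over performed procedures (p = 0.60) and 71.7% over ten attempts (p = 0.54).

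**The case against.** Several points on the other side stand.

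- **The final denominator is inferred.** A reader might infer that the protocol counts the feasibility rate only over completed procedures. It does not say so. Sections 3 and 5 say when recruitment stops and who is replaced. The statistical analysis plan, which is not at hand, could state the analysis set. Only the interim set is given in words.
- **Replacement is not open-ended.** A reader might also infer that everyone without a completed procedure is replaced and forgotten. Section 5 names three groups, and a patient who cannot be injected is not expressly among them. Removing benign frozen sections is legitimate, since no nodes are resected in them.
- **The commonest failure is probably kept.** Under Surgical procedures, a node not detected within the waiting time is treated as negative. The 50% rule makes sense only if such patients are counted.
- **The interim wording has an innocent reading.** It may mean patients who got past frozen section, and Step 1 fits that.
- **Dye reactions should be rare.** At the protocol's 0.07 to 2.7%, 28 patients would give about 0.02 to 0.8 reactions (28 × 0.0007 and 28 × 0.027), and a reaction need not end the procedure.
- **Bulky tumours.** The introduction's remark that these make the procedure difficult reports a review's general comment. It does not show that the protocol expects ligaments that cannot be reached.

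These points limit the size and certainty of the concern. They do not remove it: the interim wording, taken literally, leaves out a patient in whom the procedure could not be performed. Withdrawals on urgent medical grounds are replaced with no distinction by cause, and nothing counts a failed attempt as a failure.

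**Conclusion.** The concern holds as a risk built into the rules. For a study whose endpoint is feasibility, the protocol lets attempts that proved infeasible leave the denominator, explicitly at the interim and by implication at the end. If such attempts occur, the rate is biased upward and the 50% stop is weakened. In the illustration, two failed attempts move 82% to 90%, and one can turn a stop into a continuation when five nodes were found.

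The size rests wholly on assumed values of k and D. A reader might conclude that the primary result is inflated; the documents do not support that, because with no failed attempts the two rates coincide. The replacement and interim rules are design rules fixed in the protocol, so clarifying them there is a worthwhile, low-cost improvement.

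**What to change.** Keep recruiting to 20 completed procedures, and define a complete procedure in Section 3. Then, in Sections 3, 5 (Withdrawal and replacement; Premature termination) and 7 (Interim analysis):

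1. State the denominator of the detection rate, at the interim and at the end, as all patients in whom tracer injection was attempted or judged technically impossible at laparotomy.
2. Exclude only benign frozen sections, withdrawals before surgery, and withdrawals unrelated to the sentinel procedure. Report the number in each group separately. Counting every medical withdrawal as a failure would bias the rate downward.
3. Count patients who cannot be injected, and procedures abandoned for procedure-related reasons, as not detected.
4. Report the rate over completed procedures as a secondary result.

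The cost is wording. No procedures are added and the accrual target is unchanged, and the reasons for leaving are already to be recorded. The reported rate may be slightly less favourable.

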### **4. STUDY POPULATION**

***Population (base)***

The study will be performed in the Maastricht University Medical Centre.

- 1) Patients with a high suspicion of a malignant ovarian tumour planned for exploratory laparotomy will be asked to participate in the study. Only when a malignancy is confirmed by frozen section, the sentinel nodes will be removed prior to proceeding with a complete staging procedure.
- 2) Patients with endometrial cancer in whom a staging laparotomy is planned.

***Inclusion criteria***

- Patients with a high suspicion of a malignant ovarian tumour planned for exploratory laparotomy.
- Patients with high-risk endometrial cancer in whom a staging laparotomy is planned.
- Age between 18 and 85 years.

***Exclusion criteria***

- Previous surgery of both ovaries.
- Previous vascular surgery of the aorta, caval vein, and/or iliac vessels.
- Previous lymphadenectomy or lymph node sampling in the iliac or para-aortal region.
- History of a malignant lymphoma.
- History of a malignant tumour in the abdominal cavity.
- Previous allergic reaction to blue dye.
- Pregnant or lactating patients.
- An allergy for human albumin.

